# 7.3.2.3 Management of capillary leak syndrome (≥ Grade 3)

- a. Hold dinutuximab infusion
- b. Provide oxygen, fluids as needed
- c. Diuretics should be used with caution and hypotension avoided
- d. See Section 7.3.2.1 for management of hypotension, anemia and hypoalbuminemia
- e. Do NOT resume dinutuximab therapy if symptoms of severe capillary leak syndrome persist on the same day or subsequent days of a given cycle. Only resume dinutuximab therapy when the capillary leak syndrome resolves or requires less significant intervention (Grade 2 or less).
- f. If capillary leak resolves, may resume dinutuximab infusion at 50% rate the same day and for subsequent doses during a given cycle. The infusion may be given at the full rate at the start of subsequent cycles
- g. If mechanical ventilation (any duration) or pressor support for  $\geq$  24 hours is required due to therapy-related capillary leak syndrome, the patient should discontinue protocol therapy.

# 7.3.2.4 Management of renal insufficiency (unrelated to hypotension)

- a. Consider the possibility of renal hypoperfusion in the context of borderline hypotension; administer volume if appropriate
- b. If the patient's creatinine is elevated to  $\ge 2$  x the upper limit of normal for age/gender (see table in Section 3.2.6.2) and elevation persists despite optimized fluid management, hold dinutuximab
- c. Modify dosing of concomitant medications that may contribute to or be affected by renal insufficiency
- d. When urine output returns to normal and creatinine returns to < 2 x upper limit of normal for age/gender, resume dinutuximab at 50% rate. If renal function normalizes by the following day, dinutuximab may be administered at full rate. If renal function is not sufficiently improved (urine output normal and creatinine < 2x ULN for age/gender) by Day 7, no further dinutuximab should be given during that cycle of therapy. If renal function has normalized by the planned start date for the next cycle, retreatment with dinutuximab is permitted

# 7.3.2.5 Management of hyponatremia (≥ Grade 3; Na < 130 mEq/L and symptomatic or 120-124 mEq/L regardless of symptoms)

- a. Change hypotonic fluids to isotonic fluids as compatibilities permit
- b. Avoid administration of oral free water
- c. Correct fluid losses due to diarrhea
- d. 3% saline is only indicated in the following settings:
  - hyponatremia leading to seizure
  - drop in sodium level > 10 points in 6 hours or less
  - sodium level < 117 mEq/L
- e. If Grade 4 hyponatremia persists despite optimal fluid management, discontinue dinutuximab for the remainder of the cycle. Sodium should be monitored closely during the next cycle of therapy. If hyponatremia improves to Grade 2 or better, or baseline, empiric dose reduction is not required at the start of the next cycle of therapy, though dinutuximab would again be discontinued if Grade 4 hyponatremia were to persist despite optimal fluid management. In such cases, patient should discontinue protocol therapy.

# 7.3.2.6 Management of fever in the absence of hypotension

- a. Administer antipyretics
- b. Adjust fluids to account for insensible losses if fever is persistent
- c. Obtain blood culture
- d. Administer empiric antibiotics if suggested by institutional policy

# 7.3.2.7 Management of treatment-related pain

- a. No further dinutuximab therapy should be given to patients who experience treatment related Grade 3 pain that cannot be controlled by narcotics during a given cycle. Treatment with gabapentin or similar agent should be initiated if not already being administered. If pain that is not controlled with narcotics recurs during a subsequent cycle, the patient should discontinue protocol therapy
- b. For patients with treatment-related Grade 3 pain requiring intravenous narcotics for ≥ 48 hours following completion of dinutuximab therapy, gabapentin or similar agent should be initiated if not already being administered. If pain requiring prolonged intravenous narcotics (≥48 hours following completion of dinutuximab therapy) recurs during a subsequent cycle despite this intervention, the patient should discontinue protocol therapy.

# 7.3.2.8 Management of visual changes

- a. Dinutuximab may cause impaired accommodation and/or dilated pupils with sluggish light reflex with or without photophobia. No dose modifications, dose reductions, or changes in infusion rate should be made unless there is associated vision loss. If this occurs in conjunction with Grade 3 decrease in vision, dinutuximab should be discontinued. If visual loss improves to Grade 1 or better before the next immunotherapy course is due, the patient should receive dinutuximab at a dose that is 50% reduced compared to the prior dose. If the lower dose of dinutuximab is tolerated without worsening of ocular toxicity, full dose dinutuximab should be given in subsequent courses. If visual toxicity worsens, the patient should discontinue protocol therapy.
- b. Dose reductions for dilated pupils or changes in accommodation without vision loss are not required.

# 7.3.2.9 Management of serum sickness

- a. Identification of serum sickness signs and symptoms include arthralgias/arthritis, splenomegaly, lymphadenopathy, glomerulonephritis in the presence of persistent fevers, cutaneous eruptions.
- b. Serum sickness typically develops 1 to 3 weeks after administration of the causative agent but can develop within 12-36 hours in patients who have previously been sensitized to the causative agent.
- c. Patients with  $\geq$  Grade 3 serum sickness should discontinue protocol therapy.
- d. For Grade 2 serum sickness, antihistamines should be prescribed.

## 7.3.2.10 Management of neurotoxicity

- a. Patients who develop Grade 4 neurotoxicity should discontinue protocol therapy.
- b. Dinutuximab should be discontinued for the remainder of the current cycle of therapy for patients who develop Grade 3 sensory neuropathy or Grade 3 motor neuropathy. If abnormalities resolve by start of next cycle of therapy, the patient may receive 50% dose of dinutuximab (i.e., dinutuximab dose 8.75 mg/m²). If symptoms do not completely resolve or recur with dinutuximab then the patient should discontinue protocol therapy.

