### 6.5 Criteria for Removal from Protocol Therapy and Off Study Criteria

# **6.5.1** Criteria for Removal from Protocol Therapy

In the absence of treatment delays due to adverse event(s), treatment may continue for to a maximum of 12 cycles (9 months of combination therapy) [except in cohort B4, resectable, pulmonary only relapsed osteosarcoma, who may continue combination therapy for a total of 5 cycles after pulmonary resection] or until one of the following criteria applies:

Disease progression

- Intercurrent illness that prevents further administration of treatment.
- Unacceptable adverse event(s), including, but not limited to, any one of the following:
  - o Patients who have Grade 4 infusions reactions occurring with the first dose of Hu5F9-G4 (magrolimab) or dinutuximab will be permanently discontinued from treatment.
  - Patients who receive Hu5F9-G4 (magrolimab) premedication with corticosteroids and still have a Grade 3 or 4 infusion reaction on subsequent doses will generally be permanently discontinued from treatment, unless continued therapy is approved by the Study PI, Site PI and Sponsor.
  - O Patients who receive dinutuximab and experience any of the AEs listed in Table 8: Adverse Reactions Requiring Permanent Discontinuation of Dinutuximab

or recur after appropriate management as outlined in Section 7.3.2.

- Patient who develops a DLT during the "single agent Safety Lead-In" will be removed from additional therapy on this study.
- General or specific changes in the patient's condition render the patient unacceptable for further treatment in the judgment of the investigator.
- Clinical progression of disease
- Patient non-compliance
- Pregnancy
  - All women of childbearing potential should be instructed to contact the investigator immediately if they suspect they might be pregnant (e.g., missed or late menstrual period) at any time during study participation.
  - The investigator must immediately notify CTEP in the event of a confirmed pregnancy in a patient participating in the study.
- Termination of the study by sponsor
- The drug manufacturer(s) can no longer provide the study agents.

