#### **7.3.1** Discontinuation of Dinutuximab

The administration of dinutuximab will be discontinued for the following adverse events that are possibly, probably or definitely related to dinutuximab administration:

Table 8: Adverse Reactions Requiring Permanent Discontinuation of Dinutuximab

Severity	Adverse Reaction
Grade 3 or 4	Anaphylaxis
Grade 3 or 4	Serum sickness
≥Grade 3	Pain unresponsive to maximum supportive measures
Grade 4	Sensory neuropathy
Grade 3	Sensory neuropathy that interferes with daily activities for more than 2 weeks
≥Grade 3	Peripheral motor neuropathy
≥Grade 3	Decrease in vision if not improved to Grade 1 or better before next dose is due.
Grade 4	Hyponatremia despite appropriate fluid management

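### Sections 7.3.2.10(b) and 7.3.2.5(e) leave re-treatment with dinutuximab open after two events for which Table 8 requires a permanent stop

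*Combined protocol and SAP*

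**What the plan says.** Section 7.3.1 is mandatory: "The administration of dinutuximab will be discontinued for the following adverse events", followed by Table 8, titled "Adverse Reactions Requiring Permanent Discontinuation of Dinutuximab". Two of its rows matter here: "Peripheral motor neuropathy" at Grade 3 or higher, and "Hyponatremia despite appropriate fluid management" at Grade 4. Section 6.5.1 lists among the unacceptable events that end protocol therapy "Patients who receive dinutuximab and experience any of the AEs listed in Table 8", and then continues "or recur after appropriate management as outlined in Section 7.3.2".

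Section 7.3.2 gives management by event. Paragraph 7.3.2.10(b) covers Grade 3 sensory and Grade 3 motor neuropathy together. It withholds dinutuximab for what is left of the cycle and then says "If abnormalities resolve by start of next cycle of therapy, the patient may receive 50% dose of dinutuximab" (8.75 mg/m²). Protocol therapy ends if symptoms do not fully resolve, or if they return on dinutuximab. Paragraph 7.3.2.5(e) covers Grade 4 hyponatremia that optimal fluids have not corrected. It withholds dinutuximab for the rest of the cycle, asks for close sodium monitoring in the next one, requires no empiric dose reduction if the event has improved to Grade 2 or better or to baseline, and ends protocol therapy if the event happens again.

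**The concern.** For the same event, one part of the protocol says never again and another says next cycle is possible. Staff managing an event are likely to open the paragraph headed for that event, and for these two events it gives the less protective answer. A site that stops permanently complies with every section. A site that uses the option in Section 7.3.2 can re-treat a patient whom Table 8 and Section 6.5.1 remove.

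At stake is re-exposure in a largely pediatric population (entry from age 2). The protocol's own note on the combination, at the end of Section 10.1.1.2, names motor dysfunction and lasting peripheral-nerve damage as theoretical risks. Uneven handling between sites would also show up in the planned tabulation of reasons for stopping therapy (Section 9.2.1).

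**Working it through.** The plan states no figure on this point, so the check sets the texts side by side and then sizes the exposure.

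1. **Scope.** Sections 7.3.1 and 7.3.2 use the same attribution threshold (at least possibly related to dinutuximab), so one event falls under both. No clause says which prevails.

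2. **Grade 3 motor neuropathy.** Table 8: permanent stop, with no condition on duration or resolution. Section 7.3.2.10(b): stop for the cycle, half dose next cycle if resolved. These conflict.

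3. **Grade 4 hyponatremia refractory to fluids.** Table 8: permanent stop, with no exception for later improvement. Section 7.3.2.5(e): stop for the cycle, with next-cycle dosing implied. The closing instruction in (e) to end protocol therapy follows the clause about a repeat event. If it applied to the first event, the sentences on next-cycle monitoring and dosing would have no purpose. These conflict.

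4. **Is a resolution condition implied?** Table 8 states one where it wants one. The vision row reads "Decrease in vision if not improved to Grade 1 or better before next dose is due", and Section 7.3.2.8 matches it. The two rows at issue have no such condition.

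5. **Sensory neuropathy is not part of the point.** Table 8 stops permanently at Grade 3 only if daily activities are affected for more than 2 weeks, so 7.3.2.10(b) is mostly compatible. The overlap is narrow: in a 21-day cycle with dinutuximab on Days 2 to 5, an event starting on Day 2 and lasting 15 to 20 days could meet the row and still clear before the next cycle.

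6. **Section 6.5.1.** The word *or* between its two limbs makes recurrence a further trigger. It does not qualify the Table 8 limb.

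7. **Timing.** In Cycle 1 both events are DLTs: hyponatremia under Section 6.3(j), and motor neuropathy because no exception in 6.3 covers it. The conflict therefore matters mainly afterwards, up to 12 − 1 = 11 cycles outside Cohort B4.

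8. **Size.** Maximum enrollment (Section 9.3.3): 12 + 3 × 20 + 10 = 82.
   - Motor neuropathy, any grade, is listed below 3% in the dinutuximab risk list (Section 10.1.1.2): 0.03 × 82 = 2.46, so fewer than 2.5 patients. Those who are Grade 3, past Cycle 1 and resolved in time are a subset.
   - Hyponatremia, any grade: at most 0.20 × 82 = 16.4 from the risk list, or at least 0.25 × 82 = 20.5 from Section 7.3. Neither figure measures the Grade 4 refractory event, whose rate the documents do not give. If it were 1% to 5% of patients (an assumption for illustration, not a bound), that would be 0.01 × 82 = 0.8 to 0.05 × 82 = 4.1 patients.

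**The case against.** The strongest reply is that the contradiction does little harm in practice. The motor-neuropathy wording is permissive, and the hyponatremia paragraph only implies re-treatment. Several other controls stand in the way:

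- Table 8 is itself mandatory.
- Repeat cycles are conditional on no unacceptable toxicity, with a pointer to Section 6.3 (footnotes to Tables 5 and 6 and to the study calendars). Section 6.2.1.2 allows Cohorts B1 to B3 their 12 cycles only without DLT.
- Grade 4 hyponatremia exceeds the Grade 3 reporting exception for dinutuximab, so it must be reported within 24 hours, and the report goes automatically to the Principal Investigator.
- The Principal Investigator follows toxicity in real time (Section 6.4), and study leadership reviews data weekly (Section 13.1.2).
- Section 7 requires central consultation in its Grade 3 paragraph, which reaches motor neuropathy.

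It can also be said that the documents do not show which text the sponsor meant. Section 7.3 defers to prescribing information for detail, and that is not available here.

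Most of this stands and lowers the risk. It does not remove the contradiction: whoever is consulted finds both answers in the protocol. Uncertainty about intent is a reason to offer two ways of aligning the text, not a reason to leave it unaligned.

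**Conclusion.** The inconsistency is real for two events, Grade 3 peripheral motor neuropathy and fluid-refractory Grade 4 hyponatremia. It is a safety and consistency defect worth correcting, with few patients likely to be affected. The motor-neuropathy figure rests on a single-agent rate; the protocol warns that a combination may worsen known events, so it is not a firm ceiling for this regimen.

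A reader might infer more than the documents support:

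- **That the protocol orders re-treatment.** It permits it in one case and implies it in the other.
- **That Section 6.5.1 is the only barrier to restarting after hyponatremia.** Table 8, the toxicity condition on repeat cycles, expedited reporting and central oversight also apply.
- **That Grade 3 sensory neuropathy is in general conflict.** It is not, apart from the narrow overlap described in the working.
- **That dose finding is compromised.** Section 6.3 classifies both Cycle 1 events as DLTs whichever management text is followed, so DLT counts, sample size and error rates do not change.

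**What to change.** **Default, matching Table 8 and Section 6.5.1.** In 7.3.2.10(b), limit both the stop-for-cycle sentence and the re-treatment sentence to Grade 3 sensory neuropathy that does not meet Table 8. Editing the re-treatment sentence alone would not work, because motor neuropathy is named in the sentence before it. Then add: *Patients with Grade 3 or higher peripheral motor neuropathy should permanently discontinue dinutuximab and be removed from protocol therapy (Table 8, Section 6.5.1).* Replace 7.3.2.5(e) with: *For Grade 4 hyponatremia not corrected by optimal fluids, permanently discontinue dinutuximab and remove the patient from protocol therapy (Table 8, Section 6.5.1).* The removal clause is needed because the present paragraph's only instruction to end protocol therapy would otherwise be lost.

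**Alternative, if the sponsor's clinicians intend re-treatment.** Add explicit resolution conditions to those two Table 8 rows, on the model of the vision row. Section 6.5.1 inherits them by reference. Section 6.3 is untouched, since it borrows from Table 8 only for pain and sensory neuropathy.

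**Cost.** A wording amendment to two paragraphs or two table rows, and a notice to sites. Nothing changes in sample size, DLT rules or error rates.

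In the same amendment, the exception to the 14-day delay limit in Section 6.4 should stop pointing to Section 6.6, which deals with follow-up. That is a separate cross-reference correction and adds no weight to this point.

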#### 8 AGENT INFORMATION

A list of the adverse events and potential risks associated with the investigational or commercial agents administered in this study can be found in Section 10.1.

# 8.1 CTEP IND Agent(s)

# **8.1.1** Hu5F9-G4 (magrolimab), NSC 809249

Other names: Magrolimab or 5F9

Classification: A monoclonal antibody CD47 inhibitor

**CAS Registry Number**: 1682749-68-3

**Molecular Formula**: C6462H9960N1718O2027S48 **M.W.**: 145687.6 Daltons (predicted)

**Mode of Action**: Phagocytosis of tumor cells is blocked when CD47, a cell surface glycoprotein widely expressed by cancer cells, binds to the receptor, SIRPα, found on innate immune system cells like macrophages and dendritic cells. Hu5F9-G4 (magrolimab) blocks the binding of this 'don't eat me' signal which then allows the activation of macrophages to phagocytose cancer cells through the induction of pro-phagocytic signaling. Nonclinical studies show that CD47 inhibition combined with other anti-tumor antibodies like rituximab or cetuximab has the potential to provide synergistic pro-phagocytic signaling to macrophages.

**Description:** Hu5F9-G4 (magrolimab) is a recombinant humanized IgG4 monoclonal antibody of the IgG4 kappa isotype containing a Ser-Pro substitution in the hinge region of the heavy chain. It comprises a disulfide linked glycosylated tetramer, consisting of 2 identical 444 amino acid heavy gamma chains and 2 identical 219 amino acid kappa light chains.

**How Supplied**: Hu5F9-G4 (magrolimab) injection is an investigational agent supplied by Gilead and distributed to investigators by the CTEP Division of Cancer Treatment and Diagnosis (DCTD), NCI as 200 mg/10 mL (20 mg/mL) single-use vials in a type I borosilicate glass vial with butyl rubber stopper and aluminum seal. Hu5F9-G4 (magrolimab) is a sterile, clear to slightly opalescent, colorless to slightly yellow, preservative-free liquid in 10 mL vials. The product is formulated in 0.01% (weight/volume [w/v]) polysorbate 20, 5% (w/v) sorbitol, 10 mM sodium acetate, pH 5.0, and sterile water for injection. Hu5F9-G4 (magrolimab) is provided to the NCI under a Collaborative Agreement between the Pharmaceutical Collaborator and the DCTD, NCI (see **Section Error!** Reference source not found.).

**Preparation:** Acceptable IV bags are: Polyvinyl chloride (PVC) preferably without DEHP or non-PVC alternatives such as ethylene vinyl acetate, polypropylene (ViaFlo®) or combination of ethylene and polypropylene (Excel® or IntraVia®).

The following proprietary closed system transfer devices (CSTDs) are compatible with magrolimab: PhaSeal, PhaSea Optima, Equashield, ChemolockT, SmartSite with Texium and Spiros.

- For doses of 1 mg/kg or less, dilute dose in 250 mL 0.9% sodium chloride
- For doses greater than 1 mg/kg, dilute dose in 500 mL 0.9% sodium chloride. A 250 mL 0.9% sodium chloride may be used to prepare doses for subjects with volume restriction. Refer to the table below for the total infusion volumes for each age group.
- Obtain the required number of vials from stock and examine them for discoloration, cloudiness or particles. Do not use if particulate matter or discoloration is noted.
- Remove the equivalent Hu5F9-G4 (magrolimab) calculated dose volume from the 250 mL or 500 mL IV bag if using a prefilled 0.9% sodium chloride IV bag.

- Add the calculated dose volume of Hu5F9-G4 (magrolimab) into the 0.9% sodium chloride IV bag.
- Gently invert the IV bag 3-6 times to mix the solution. Avoid foaming IV solution. If particulate matter or discoloration occurs, do not use the IV preparation.

## Total Infusion Volume per Age Group

Age Group	\ \ /	Maintenance Infusion Volume (mL) – infused over 2 hours (+/- 10 minutes)
≥1 year to < 2 years	50	100
2 years to < 6 years	250	250
6 years to < 12 years	250	250
12 years to < 18 years	250	500
Adult	250	500

The prepared IV solution can be stored at  $25^{\circ}$  C and must be used within 8 hours of preparation. Discard the prepared IV solution if exceeding 8 hours. Do not refrigerate the prepared IV solution. There is no stability data to support the prepared IV solution stored at  $2^{\circ}$ C -  $8^{\circ}$ C ( $36^{\circ}$  F to  $46^{\circ}$  F).

Do not mix with any other drug in the infusion bag or administration set.

Storage: Store vials at 2°C - 8°C (36° F to 46° F) in the original carton, protected from light. Do not freeze.

If a storage temperature excursion is identified, promptly return Hu5F9-G4 (magrolimab) to 2°C -8°C (36° F to 46° F) and quarantine the supplies. Provide a detailed report of the excursion (including documentation of temperature monitoring and duration of the excursion) to [contact] for determination of suitability.

**Stability:** Shelf-life stability studies of the intact or unused vials are on-going.

*CAUTION:* The single-use injectable vial contains no antibacterial preservatives. Therefore, it is advised that the reconstituted product be discarded 8 hours after initial entry.

**Route of Administration:** Intravenous. Do not administer as an IV bolus.

**Method of Administration:** A priming dose of Hu5F9-G4 (magrolimab) is required in Cycle 1 Day 1. The priming dose (1 mg/kg) will be infused over 3 hours (+/- 30 minutes) via a peripheral or central line. Protecting IV bag from light is not required. In-line IV filter set is not required. Subsequent IV doses are to be infused over 2 hours (+/- 10 minutes).

**Patient Care Implications:** Advise men and women of reproductive potential to use effective contraception while receiving study treatment and for 4 months after the last dose of Hu-5F9. Male patients whose partners are pregnant may continue study treatment and should use barrier method contraception (condom) to prevent exposing the fetus. Refer to the protocol Section 6.8 for specific guidance.

Since infusion reactions can occur, all patients should be monitored for 1-hour post-infusion for the priming dose. Patients who experience any treatment-related adverse events during the observation period should be further monitored as clinically appropriate (e.g., for up to 24 hours post-dose). All patients should be monitored for 1-hour

post-infusion for Cycle 1. Further doses (Cycle 2+) do not require post-infusion observation. Patients who experience any treatment-related AEs during the observation period should be further monitored as clinically appropriate. Follow the protocol's instructions for managing infusion symptoms and hypersensitivity to Hu5F9-G4 (magrolimab).

**Availability:** Hu5F9-G4 (magrolimab) is an investigational agent supplied to investigators by the Division of Cancer Treatment and Diagnosis (DCTD), NCI.

If the study agent is provided by the NCI under a Collaborative Agreement with the agent manufacturer, the text below must be included in the protocol. Information on the study agent's Collaborative Agreement status will be provided in the approved LOI response letter.

Hu5F9-G4 (magrolimab) is provided to the NCI under a Collaborative Agreement between the Pharmaceutical Collaborator and the DCTD, NCI (see Section Error! Reference source not found.).

